2 GENERAL INFORMATION

2.1 Background details

All study data will be transferred to a SAS database (version 9.4 or later) for statistical analysis purposes. Data will be imported from the Data Capture System OPVerdi via validated SAS programs. If applicable external data will also be transferred to SAS for presentation of these data in the statistical analyses.

The SAP will be finalized before database review meeting after agreement with the Sponsor.

2.2 Deviations from the trial protocol with regard to statistical analyses

Due to the reporting of non-confirmed eligibility, the primary and secondary efficacy analyses will also be performed for the mFAS (see section 3.3).

Contrary to initial assumptions, patients may have documented 0 bleeding episodes during the prophylactic treatment phase. This would contradict the assumption of a log-normally distributed TABR and make the calculation of logarithms of the TABRs impossible. Hence, instead of the originally planned paired t-test for the log-transformed data, now the use of a negative binomial counting regression model (GLIM) with treatment regimen as main effect and treatment period as offset parameter is implemented for the analysis of the primary efficacy parameter.

Such counting regression models will also be used for the analysis of similarly defined secondary and exploratory endpoints (e.g. SABR).

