9.2.2 Efficacy Analysis Plan

The analysis of the efficacy of prophylactic treatment with *Wilate* will be based on the FAS and the PP set.

Primarily, all obtained data on treatment characteristics (IMP dosages, frequencies, total consumption), VWF:Ac and FVIII:C incremental IVR of *Wilate* over time and BEs (duration, frequency, efficacy assessment) will be described using summary statistics.

Whenever sufficient reliable and comparable data on secondary endpoints (see **Section 3.1.2**) or exploratory endpoints (see **Section 3.1.3**) are available for similar historical on-demand treatment periods, exploratory statistical comparisons of these endpoints to on-demand treatment periods will be considered.

Efficacy of Prophylactic Treatment with Wilate

The efficacy of prophylactic treatment with *Wilate* will be assessed by comparing each patient's individual ABR under prophylactic treatment in this study with the ABR recorded for the same patient in a previous, non-interventional, study or with the ABR that can reliably be obtained from the patient's bleeding documentation.

Efficacy of prophylactic treatment with *Wilate* will be statistically evaluated by analysing the primary endpoint, i.e., demonstration that the TABR during prophylactic treatment lowers the patients' TABR during on-demand treatment by more than 50%.

To test whether the mean TABR during prophylactic treatment ($TABR_{pr}$) is less than half the historical mean TABR during on-demand treatment ($TABR_{od}$), the following pair of hypotheses will be tested using a paired t-test assuming log-normally distributed data:

$$H_0: \text{mean}(TABR_{pr} / TABR_{od}) \geq 0.5 \text{ vs } H_1: \text{mean}(TABR_{pr} / TABR_{od}) < 0.5$$

at a one-sided alpha level of 2.5%. A corresponding two-sided 95% CI for the TABR will also be provided.

To assess the qualitative robustness of the inferential result, the hypothesis will additionally be tested with the Wilcoxon (matched-pair signed rank) test on the log-transformed bleeding rate as a distribution-free alternative. Also, a 95% Hodges-Lehmann CI for the median difference will be reported.

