1.5 Planned sample size

Overall, 28 patients will be enrolled in this study, including at least 5 patients with VWD type 3, at least 5 patients aged 6–11 years, and at least 5 patients aged 12–16.

Assuming a mean total annualized bleeding rate (TABR) ratio (TABR_{pr} / TABR_{od}) of 0.25 with a correlation of 0.5 between the two treatment regimes, a coefficient of variation of 10 in on-demand treatment, and a coefficient of variation of 10 in prophylactic treatment, 25 patients will be needed to reject the null hypothesis

Statistical Analysis Plan	Version 6.0		Page 7 of 24
Sponsor	Octapharma	Protocol No	WIL-31

$$H_0: \text{mean}(\text{TABR}_{\text{pr}} / \text{TABR}_{\text{od}}) \geq 0.5$$

in favor of

$$H_1: \text{mean}(\text{TABR}_{\text{pr}} / \text{TABR}_{\text{od}}) < 0.5$$

with a type one error of 0.025 and power of 80% using a paired t-test for log-transformed data.

TABR_{pr} is defined as the total annual bleeding rate in the prophylactic treatment and TABR_{od} is defined as the total annual bleeding rate in the matching on-demand treatment period.

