4.1.4 Use of measurements from on-demand non-interventional run-in study (WIL-29)

Apart from analyzing the efficacy of Wilate in the prophylactic treatment of VWD based on annualized bleeding rates, it is also of interest to compare data with annualized bleeding rated of the same patients under an on-demand treatment schedule. To achieve this, data from those patients that also participated in a previous on-demand run-in study (WIL-29) will be used in the analysis data for the current study. This includes duration of On-demand phase, number of bleeding episodes and annualized bleeding rates for total, spontaneous, traumatic, and heavy menstrual bleeds.

For females with childbearing potential, it is of interest to compare their differences in median PBAC scores under prophylaxis with scores under on-demand treatment. For this purpose, all total PBAC scores collected during study WIL-29 will be stored in the WIL-31 database and the Wilcoxon matched pair sign-rank test will be used for statistical comparison.

The statistical methods for such exploratory comparisons of on-demand to prophylactic treatment schedule will be based on paired, or repeated-measurement data.

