4.7.1 Primary Endpoint

Primary objective of this study is to demonstrate that the total annualized bleeding rate (TABR) during prophylactic treatment lowers the patients' TABR during on-demand treatment by more than 50%.

TABR will be calculated as the total number of spontaneous, traumatic and other bleeds (excluding menstrual bleeds) in the time period between first prophylactic dose of IMP and the day of the last dose of IMP (+ 2 days wash-out), divided by the duration (in years) between first dose of prophylactic IMP and the day of last dose of IMP (+ 2 days wash-out). Surgery periods, and BEs occurring within these periods, will be excluded from the calculation of TABR. Menstrual bleeds of any severity will not be included in this calculation. In female patients with child-bearing potential heavy menstrual bleeds will be reported and analyzed separately.

For this efficacy assessment the individual annualized bleeding rates under prophylactic treatment in this study will be compared to the annualized bleeding rates recorded for the same patient during a previous, non-interventional study, (WIL-29).

To test whether the mean TABR during prophylactic treatment ($TABR_{pr}$) is less than half the historical mean TABR during on-demand treatment ($TABR_{od}$), the following pair of hypotheses will be tested in the context of negative binomial counting regression model:

$$(*) H_0: \text{mean}(TABR_{pr} / TABR_{od}) \geq 0.5 \quad \text{vs} \quad H_1: \text{mean}(TABR_{pr} / TABR_{od}) < 0.5$$

at a one-sided alpha level of 2.5%. A corresponding two-sided 95% CI for the different TABRs and their ratio will also be provided.

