6 DERIVATIONS AND TRANSFORMATIONS

6.1 Formulas for derived variables

Variable	Description
Durations between two dates	Later date minus earlier date plus 1, expressed in days. (Remark: Duration will be 1, if both dates are the same.)
On-Demand period (days)	(Date of study completion – date of screening + 1) - Surgery period. Applicable for historical data from WIL-29
Surgery Period _{od} (days)	Formula for surgery period under on-demand treatment correspond to formula for surgery period under prophylactic treatment but replacing “IMP” by “VCP (von Willebrand factor containing product)”. Applicable for historical data from WIL-29
Prophylactic treatment phase (days)	((last date of IMP + 2 OR completion date, whatever occurred earlier) – first date of prophylactic IMP +1) – Surgery period.
Surgery Period (days)	Individual surgery period: last date of IMP in context of surgery (reason = “Prophylaxis after surgery” or “Surgery”) – date of surgery + 1 or 1 day (i.e. day of surgery) in case surgery not treated/no treatment information available. Surgery period: Sum of individual surgery periods per subject. All BEs at day of surgery with onset after start of surgery and all BEs occurring under post-operative prophylaxis (reason = “Prophylaxis after surgery”) will be excluded from the calculation of ABRs
Annualized Bleeding Rates On-Demand (ABR _{od})	Formulas for ABR under on-demand treatment correspond to formulas for ABR under prophylactic treatment but replacing “prophylactic treatment phase” by “on-demand period”. Individual annualized bleeding rates under on-demand period will be taken from calculated rates in study WIL-29 for all subjects along with total number of bleedings
Total Annualized Bleeding Rate Prophylaxis (TABR _{pr})	Number of bleedings under prophylactic treatment phase (except menstrual bleedings) / (prophylactic treatment phase /365.25)
Spontaneous Annualized Bleeding Rate Prophylaxis (SABR _{pr})	Number of spontaneous bleedings under prophylactic treatment phase /(prophylactic treatment phase/365.25)
Traumatic Annualized Bleeding Rate Prophylaxis (TRABR _{pr})	Number of traumatic bleedings under prophylactic treatment phase / (prophylactic treatment phase/365.25)
Heavy Menstrual Annualized Bleeding Rate Prophylaxis (HMABR _{pr})	Heavy Menstrual Annualized Bleeding Rate: Number of heavy menstrual bleedings under prophylactic treatment phase / (prophylactic treatment phase/365.25)

Statistical Analysis Plan	Version 6.0		Page 22 of 24

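### The SAP does not say how a patient's two bleed counts are linked in the primary negative binomial model; fitted literally it ignores the pairing, which can make the test over-conservative

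*SAP*

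**What the plan says.** The protocol's primary test (9.2.2) was a paired t-test on log-transformed TABR, supported by a rank test: "the hypothesis will additionally be tested with the Wilcoxon (matched-pair signed rank) test on the log-transformed bleeding rate".

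SAP 2.2 explains that patients may have no bleeds on prophylaxis, so logarithms cannot be taken, and substitutes a "negative binomial counting regression model (GLIM) with treatment regimen as main effect and treatment period as offset parameter". SAP 4.7.1 adds only that "the following pair of hypotheses will be tested in the context of negative binomial counting regression model", at one-sided 2.5%. Neither section names a patient effect, a repeated-measures or cluster structure, or a type of standard error.

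The data are paired throughout. SAP 4.7.1 compares rates within the same patient, and 6.1 states that the individual on-demand rates "will be taken from calculated rates in study WIL-29 for all subjects along with total number of bleedings".

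SAP 4.1.4, on the use of WIL-29 data, lists "annualized bleeding rates for total, spontaneous, traumatic, and heavy menstrual bleeds" and then says: "The statistical methods for such exploratory comparisons of on-demand to prophylactic treatment schedule will be based on paired, or repeated-measurement data". It names a specific test only for PBAC scores.

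SAP 1.5 keeps the sample size of the earlier test, "with a correlation of 0.5 between the two treatment regimes" and "with a type one error of 0.025 and power of 80% using a paired t-test for log-transformed data".

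**The concern.** The within-patient comparison is the study's only control, and the primary claim rests on one ratio, its interval and its p-value. With two records per patient, the variance of the log rate ratio contains a covariance term. A model with regimen and offset alone, fitted to rows treated as independent, leaves that term out.

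Two programmers could follow this SAP faithfully and differ. One would fit the model of 2.2 to independent rows. The other would read 4.1.4 as governing the primary comparison and cluster by patient. With the same dispersion and an independence working correlation the point estimates agree, but the intervals and p-values do not. SABR, TRABR and HMABR inherit the gap, because 4.7.2 and 4.7.3 tie them to the TABR approach.

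Separately, a reader of 1.5 would take 80% power to describe the current primary test. It does not.

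**Working it through.** **1. The plan's own sample size.** Inputs from SAP 1.5: ratio 0.25 against 0.5, CV 10 in both regimens, correlation 0.5, one-sided 0.025.
- Log variance per regimen: ln(1 + 10²) = ln 101 = 4.615.
- Log covariance, with the correlation on the raw scale: ln(1 + 0.5 × 10²) = ln 51 = 3.932.
- SD of the log difference: √(2 × 4.615 − 2 × 3.932) = 1.169.
- Difference to detect: ln(0.5/0.25) = 0.693.
- Noncentral t: n = 25, power 81.2%.

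The stated 25 is reproduced. It needs the raw-scale reading, which implies a log-scale correlation of 3.932/4.615 = 0.85. A correlation of 0.5 on the log scale would need 78. The calculation therefore describes a paired test on logs and nothing else.

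**2. What leaving out the pairing does.** Var(log ratio) = V_od + V_pr − 2·Cov. If the two variances are equal and the two log-rate estimates have correlation r, independence SE / true SE = 1/√(1 − r). At r = 0.5 this is 1.41. Omitting a positive covariance can only enlarge the SE.

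**3. Simulation at n = 25.** From the documents: 12 months of prophylaxis and at least 6 months on demand (0.5 year used). Assumed, because the documents do not give them:
- patient-rate CV 0.7–1.0;
- treatment-effect CV 0.5 or 1.0;
- 24 on-demand bleeds a year, or a source mean of 8 per 6 months when the six-bleed entry rule truncates the analysed count.

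Both truncation cases are shown. The documents do not say whether the WIL-29 window is the one in which the six bleeds were counted, and the second entry route has no minimum. The target is the ratio of mean rates. *As written* is a common-dispersion negative binomial fit with a Wald test. *Clustered* is a robust SE by patient with the Mancl-DeRouen correction and t(n−1). There were 4,800 runs per cell.

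| Scenario | Model SE / true SE | One-sided error at 0.5, as written | Power at 0.25, as written | Power, clustered (held to a true 2.5%) |
|---|---|---|---|---|
| No truncation, effect CV 0.5 | 1.5–1.9 | 0.1–0.4% | 70–92% | 97–99% (96–98%) |
| No truncation, effect CV 1.0 | 1.1–1.2 | 2.6–3.1% | 58–73% | 74–79% (55–65%) |
| Truncation, effect CV 0.5 | 1.1–1.35 | 0.8–1.5% | 98–99.5% | 99–99.5% (99%) |
| Truncation, effect CV 1.0 | 0.9–1.0 | 5.1–5.5% | 83–86% | 82% (68–71%) |
| Plan's inputs: log-normal, CV 10, correlation 0.5 (24/year assumed) | 0.96–0.98 | 2.7% | 22% | 50% (14%) |

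At n = 28 the pattern is the same; the first row has SE ratio 1.5–1.9 and power 76–95% against 98–99.5%.

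**4. A different data-generating model.** Correlated gamma frailties, 24 bleeds/year, dispersion 1 in both periods, frailty correlation 0.5. At ratio 0.5 the model SE was 0.289 and the true SE 0.223, a ratio of 1.30, with one-sided error 0.6%. At ratio 0.25, power was 71% as written and 86% clustered. The clustered test's error was about 4%.

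**5. Where the excess error comes from.** In that second model, with zero correlation and dispersion 0.5 on demand against 4 on prophylaxis, the SE ratio was 0.83 and the error 8.3%. There is no pairing to ignore in that cell, so the excess comes from the shared dispersion parameter and small n. The truncated, effect-CV-1.0 case behaves alike. Over repeated runs the error was 4.8–6.1% as written and 4.4–6.7% clustered. It was 2.7–3.9% with a row-level robust SE that also ignores pairing.

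**The case against.** The strongest reply is that the SAP already covers this. SAP 4.1.4 is the section on using WIL-29 data, it includes total rates, and it says the comparison rests on paired or repeated-measurement data; 4.7.1 speaks of the same patient. A repeated-measures fit is compatible with all of this. That stands as far as it goes: a reader might infer that the SAP has decided to treat the pairs as independent, and the documents do not support that. But 4.1.4 introduces these comparisons as additional, labels them exploratory and names no model for bleeding rates, so it does not settle the confirmatory test.

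A second reply is that clustering weakens error control at this size. That also stands. The clustered test ran at 2.9–6.4% one-sided in the gamma scenarios and about 12–13% at CV 10, so part of its apparent power gain is inflated error. Held to a true 2.5%, it shows a clear benefit only in the first row of the table. The remedy must state this openly.

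Third, a reader might infer that the missing patient term makes the primary test liberal and so threatens a positive result. Steps 2 and 5 show otherwise. Nor does it follow that the sample size should be redone with zero correlation, because no document plans such a test. On the plan's own CV of 10, the low power of the current model comes mainly from moving to mean rates, and clustering does not restore it.

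Finally, 2.2 openly discloses that the paired t-test was replaced, and its zero-count reason would also rule out the Wilcoxon test on log rates. What remains is that 2.2 does not list the Wilcoxon as dropped, and 1.5 does not say its power figure is superseded.

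**Conclusion.** The concern holds as a specification gap with a real consequence under one plausible reading. Fitted literally, the primary model ignores the pairing. With positive within-patient correlation and a fairly uniform effect, the SE is about 1.5–1.9 times too large, the one-sided error falls to 0.1–0.4%, and power drops from 96–98% (clustered, held to a true 2.5%) to 70–92%. With highly variable effects the loss is small or absent. The excess error of about 5% under truncation is not due to the missing patient term and is not removed by clustering.

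These sizes rest on assumed bleed rates, dispersion and effect variability, and on reading the target as the ratio of mean rates, which is what the model estimates. They show direction and order of magnitude; they do not forecast this trial's result. That the 80% power in 1.5 does not describe the model in 4.7.1 needs no simulation. The point should be fixed before the analysis is run, but it does not invalidate the study.

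**What to change.** 1. In 2.2 and 4.7.1, keep the log-link negative binomial mean model with log(period) as offset. State that the two records are clustered by patient: GEE, independence working correlation, Mancl-DeRouen-corrected robust SE, t reference with n−1 degrees of freedom. Say that 4.1.4 governs the primary comparison, and that SABR, TRABR and HMABR follow.
2. Report the independence-model interval alongside. State that at 25–28 patients the clustered test is somewhat liberal (about 3–6% one-sided in the gamma scenarios, about 12–13% at CV 10), so a borderline result must be read with both.
3. In 1.5, state that n = 25 and 80% power apply to the superseded paired log t-test, not to the current primary model.
4. In 2.2, list the protocol's Wilcoxon test on log rates as dropped. A signed-rank test on TABR_pr − 0.5 × TABR_od tolerates zeros and is an optional sensitivity analysis. It addresses a median difference. Read as a test of the ratio of means, its error was 4.5–15.3% in the gamma runs.

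A patient random intercept should not be substituted silently. When treatment effects vary it changes the estimand (mean estimate 0.38–0.47 at a true 0.5, error 7–23%).

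The cost is SAP wording and one model statement, with no new data. With the same dispersion and an independence working correlation, the point estimate is unchanged; only the SE, interval and p-value move.

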2.3 Individual protocol deviations

Any deviation from protocol will be discussed case by case before database lock whether the deviation has to be regarded as minor or as major, and whether an observed deviation will lead to exclusion from particular analysis populations.

Examples for minor protocol violations may be deviations from scheduled investigation time.

Criteria for important protocol violations will at least include:

- Any substantial violation of in- or exclusion criteria.
- Use of concomitant medication that may interfere with the assessment of efficacy.

Statistical Analysis Plan	Version 6.0		Page 8 of 24
Sponsor	Octapharma	Protocol No	WIL-31

- Substantial deviations in frequency, duration and/or dosing of the prophylactic treatment regimen.

The final decision about the classification of individual protocol deviations and their consequences regarding assignment of subjects to analysis sets will be made during the data review meeting (DRM). A complete listing of protocol deviations and the judgment for assessment of subject disposition will be approved by the Sponsor and signed before database lock. All deviations as well as the disposition of each subject will be recorded in separate database members that will become part of the study database. A description of all important protocol violations will be included in the table part of the CSR.

3 ANALYSIS POPULATIONS

The disposition of patients will be displayed according to the following analysis populations:

- Safety (SAF) set
- Full Analysis set (FAS)
- Modified Full Analysis set (mFAS)
- Per-Protocol (PP) set
- Surgery (SURG) set
- Pharmacokinetic (PK) set
- Pharmacokinetic Per-Protocol (PK PP) set

Membership of subjects will be decided upon in a DRM with the Sponsor before database lock. The proper flags for analysis sets exclusion (e.g., exclusion from PP set), will be included in the analysis datasets.

3.1 Safety Set

The **safety (SAF) set** will include all subjects who received at least one dose of IMP.

3.2 Full Analysis Set

The **full analysis set (FAS)** defined according to the intention-to-treat (ITT) principle will include all enrolled subjects who received at least one dose of IMP after the Baseline IVR Visit in adults or the Baseline PK Visit in children.

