4.3.2 Patient Replacement Policy

Drop-outs will not be replaced.

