5.4 Dose and Dosing Schedule

5.4.1 *Wilate* Dosage for PK Assessment in Paediatric Patients

For the PK assessment in paediatric patients (6–16 years), a single dose of 60 ± 10 IU/kg will be administered.

5.4.2 *Wilate* Dosage for Prophylactic Treatment

For prophylactic treatment, *Wilate* should be administered 2–3 times per week at a dose of 20–40 IU/kg BW for 12 months.

The prophylactic dose for each patient will be determined by the Principal Investigator based on each patient's clinical condition and at the following time points:

- At the Baseline IVR Visit (see Section 6.1.2) in adult patients (≥ 17 years)
In adult patients, the first prophylactic dose will be administered at the time of the baseline IVR assessment.
- At the Baseline PK Visit (see Section 6.1.4) in paediatric patients (6–16 years)
In paediatric patients, the first prophylactic dose will be administered after completion of the PK phase.

In case of unacceptably frequent spontaneous breakthrough BEs (i.e., more than 2 spontaneous BEs or 1 major spontaneous BE within a 30-day period), the dose of *Wilate* should be increased by approximately 5 IU/kg (depending on the entire content of the additional vials that need to be reconstituted). If, after a dose increase, patients still experience more than 2 spontaneous bleeding episodes, the dosing interval should be shortened from 2 times per week to 3 times per week.

5.4.3 *Wilate* Dose for the Treatment of Breakthrough BEs

The dose (and duration) of treatment of BEs will depend on the location and extent of bleeding and on the clinical condition of the patient.

Generally, 1 IU/kg BW VWF:Ac (VWF:RCo) and FVIII:C raises the plasma level by 1.5–2% of normal activity for the respective protein. Usually, about 20–50 IU *Wilate*/kg BW are necessary to achieve adequate haemostasis. This will raise the VWF:Ac (VWF:RCo) and

FVIII:C in the patients by approx. 30–100%.

The following should be used to guide dosing in the treatment of BEs:

Dose type	Minor haemorrhage*	Major haemorrhage
Loading dose	20–40 IU/kg	40–60 IU/kg
Maintenance dose	20–30 IU/kg every 12–24 hours	20–40 IU/kg every 12–24 hours
Therapeutic goal	Maintain VWF:Ac (VWF:RCo) and FVIII:C trough levels >30%	Maintain VWF:Ac (VWF:RCo) and FVIII:C trough levels >50%

*Menstrual bleeds of regular intensity (i.e., minor menstrual haemorrhage) will be considered normal and are not expected to require therapy unless deemed necessary by the investigator and/or the patient.

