6.1.2 Baseline IVR Visit (Adult Patients)

During the Baseline IVR Visit, the prophylactic dose and dosing interval of *Wilate* for each adult patient will be determined by the Principal Investigator based on the patient's clinical condition, and the first prophylactic dose will be administered after a washout period of **at least 72 hours** from the patient's latest administration of a VWF-containing product. Patients must not be experiencing any bleeding.

The following assessments will be performed:

BEFORE ANY OTHER ASSESSMENTS

- **Confirm inclusion and exclusion criteria** (to be documented in patient records)
- **QoL questionnaires** (PROMIS-29 for all patients, SF-36v2 or SF-10 as applicable)

BEFORE INJECTION

- **Weight**
- **Blood samples**
 - VWF multimer pattern for VWD type 2A and genotype for VWD type 2B [central lab]
 - Anti-parvovirus B19 antibodies [central lab]
 - Retention samples for possible virus marker and VWF/FVIII inhibitor testing [central lab]

WITHIN 60 MIN BEFORE AND 60±5 MIN AFTER INJECTION

- **Vital signs**
- **Blood samples**
 - VWF:Ac (VWF:RCO and VWF:GPIb) for IVR [central lab]
 - FVIII:C (OS and CHR) for IVR [central lab]

ANY TIME

- **Patient diary review, with documentation of PBAC** data and calculation of PBAC score by investigator (in female patients of child-bearing potential)
- **Hemophilia Joint Health Score (HJHS)**
- **Target joint(s)**
- Re-confirm commitment to using **birth control measures** (in female patients of child-bearing potential)
- Monitoring of **adverse events (AEs)**
- **Concomitant medications**

In adult patients, the first prophylactic injection of *Wilate* is administered during the Baseline IVR Visit.

In case of **home treatment**, patients will be trained in how to correctly administer the IMP and provided with IMP. Patients will be re-supplied with IMP whenever necessary during the study.

SCREENING AND BASELINE VISITS FOR PAEDIATRIC PATIENTS (6–16 YEARS)

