9.2.1 Populations for Analysis

The **safety set (SAF)** will include all patients who received at least one dose of IMP.

The **full analysis set (FAS)**, defined according to the intention-to-treat (ITT) principle, will include all enrolled patients who received at least one dose of IMP after the Baseline IVR Visit in adults or the Baseline PK Visit in children.

The **per-protocol (PP) set**, i.e., a subset of the FAS, will exclude patients with major protocol deviations which may have an impact on the evaluation of the primary study outcome parameter. Examples of major and minor protocol deviations will be described in the SAP.

The **surgery (SURG) set** will be a subset of the FAS, containing all patients who underwent a surgical procedure treated with *Wilate* during their prophylactic treatment phase.

The **pharmacokinetic (PK) set** will be a subset of the FAS, containing all patients for whom a valid PK profile was obtained at baseline.

A final decision about the classification of protocol deviations and their consequences regarding assignment of patients to analysis sets will be made during the data review meeting. Decisions and outcome will be approved by the Sponsor.

- The analysis of safety will be based on the SAF set.
- The evaluation of the primary endpoint will be performed on the FAS (ITT analysis) and on the PP set (PP analysis).
- For secondary and exploratory endpoints, ITT and PP analyses will be carried out, unless these analysis sets differ by no more than 5% of patients.
- Analysis of the efficacy and safety of *Wilate* in surgeries will be based on the SURG set.
- Analysis of the PK properties of *Wilate* will be based on the PK set.

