3.6 Pharmacokinetic Set

The **pharmacokinetic (PK) set** will be a subset of the FAS containing all subjects with a pharmacokinetic assessment.

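### Nesting the PK set in the FAS drops a child with a complete single-dose profile and no later IMP from every PK summary; the same FAS wording also treats adults and children differently

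*SAP*

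**What the plan says.** SAP 3.2 admits to the FAS enrolled subjects who "received at least one dose of IMP after the Baseline IVR Visit in adults or the Baseline PK Visit in children". Protocol 9.2.1 has the same rule and the same label: "defined according to the intention-to-treat (ITT) principle, will include all enrolled patients who received at least one dose of IMP after the Baseline IVR Visit", with the matching condition for children.

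The PK set is built on the FAS in both documents. Under protocol 9.2.1 it "will be a subset of the FAS, containing all patients for whom a valid PK profile was obtained at baseline". Under SAP 3.6 it "will be a subset of the FAS containing all subjects with a pharmacokinetic assessment". SAP 3.7 takes the PK-PP set from the PK set and there removes subjects with unconfirmed VWD, subjects with an inhibitor at the PK visit, and invalid samples or profiles.

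The timing of the first prophylactic dose differs by age. For adults, protocol 5.4 says "In adult patients, the first prophylactic dose will be administered at the time of the baseline IVR assessment", and protocol 6.1.2 agrees: "In adult patients, the first prophylactic injection of *Wilate* is administered during the Baseline IVR Visit". For children, protocol 5.4 says "In paediatric patients, the first prophylactic dose will be administered after completion of the PK phase".

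Protocol 3.2 aims for at least 6 children in each of the two age bands, at least 4 of them evaluable for PK. SAP 1.5 gives at least 5 enrolled per band. Protocol 4.3.2 states "Drop-outs will not be replaced".

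**The concern.** The FAS condition serves the efficacy question: has the patient gone on to treatment beyond the baseline visit? The PK set inherits it without needing it. Whether a child's single-dose profile is usable depends on the dose, the samples, the diagnosis and inhibitor status, and SAP 3.7 already covers the last three. Nesting in the FAS adds no quality control. It only adds a way to lose a usable profile, in age bands where each child is a large share of the data.

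The secondary concern is that one sentence sets two different entry points. A child enters the FAS with the first prophylactic dose. An adult whose only IMP is the first prophylactic dose does not enter, although SAP 4.7.1 starts the TABR period at that dose. The exclusion depends on something that happens after treatment starts, which is not what the ITT label promises. It passes to the mFAS, the primary set under SAP 4, and to the PP set.

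**Working it through.** **The plan's own figure.** The plan gives no precision calculation for PK. Its one derived number is the 25 patients of SAP 1.5. Reading the coefficient of variation of 10 as a ratio and the correlation of 0.5 on the original scale, the SD of the log ratio is √(2 × (ln 101 − ln 51)) = 1.169. The effect is ln(0.5/0.25) = 0.693. A paired t-test at one-sided 0.025 then has 81.2% power with 25 patients and 79.4% with 24, so 25 reproduces. Nothing below changes it.

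**Set membership, traced against dose timing.**

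| Patient | SAF | FAS | mFAS, PP | PK, PK-PP |
|---|---|---|---|---|
| Child: PK dose, full 72-hour profile, no later IMP | yes | no | no | no |
| Child: PK dose, then first prophylactic dose | yes | yes | if eligible | if eligible |
| Adult: first prophylactic dose at Baseline IVR Visit, no later IMP | yes | no | no | not applicable |
| Adult: as above, then any later IMP dose | yes | yes | if eligible | not applicable |

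Could the FAS wording be meant to include doses given during the baseline visit? Then every treated patient would qualify, since IMP starts at that visit in both cohorts. The FAS would equal the treated, enrolled patients and the clause would do no work. The literal reading is the one that gives it a meaning.

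**PK precision.** SAP 4.7.2 foresees exploratory 95% intervals for secondary endpoints, which include paediatric PK. The half-width of a t-interval, in SD units, is t(0.975, n−1)/√n:

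- n = 6: 2.571/2.449 = 1.05
- n = 5: 2.776/2.236 = 1.24
- n = 4: 3.182/2.000 = 1.59

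One child is 1/6 = 17% or 1/5 = 20% of a band at the stated minimum sizes. The interval widens by about 18% (6 to 5) or 28% (5 to 4).

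**Chance of keeping at least 4 per band.** The documents give no probability q that a child stops in this window, so q is an assumption, with no other PK loss. The formula is the binomial P(X ≥ 4) with success probability 1 − q.

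| q | from 6 | from 5 |
|---|---|---|
| 5% | 99.8% | 97.7% |
| 10% | 98.4% | 91.9% |
| 20% | 90.1% | 73.7% |

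For example, from 5 at q = 10%: 0.9⁵ + 5 × 0.9⁴ × 0.1 = 0.590 + 0.328 = 0.919.

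**Adult half.** By SAP 6.1, an adult with one dose has a prophylactic phase of at most (last date + 2) − first date + 1 = 3 days. If the other 27 of the SAP's 28 patients each contribute 365 days, the share of person-time is 3/(27 × 365 + 3) = 3/9,858, about 0.03%.

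**The case against.** The strongest case is that the rule rarely bites. A child must finish 72-hour sampling and then receive no IMP at all, and prophylaxis follows the PK phase. The target of 4 evaluable out of 6 already allows two losses. PK is descriptive and no test rests on it. SAP 4 lists all subject data, so the measurements stay visible. All of this stands, and it limits the weight of the point. It gives no reason for the nesting.

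Several stronger readings are tempting and are not supported:

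- That an adult enters the FAS only with a second prophylactic dose. The rule says any dose of IMP, so a later dose for a bleed or surgery also qualifies.
- That the SAP plans only 5 children per band. SAP 1.5 sets 5 as a minimum, so the 5-to-4 figures describe that minimum and not the expected number.
- That this rule takes a band below 4 evaluable. From the stated minima, one such loss leaves 5 or 4. Falling to 3 needs other losses first.
- That the FAS rule distorts the primary result. With 3 days of exposure in a model with treatment period as offset, the effect is negligible.
- That safety information is lost. Safety analyses use the SAF, which keeps these patients.

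For adults there is also a real argument for the present rule. A patient with 3 days of follow-up gives an unstable individual TABR: one bleed gives 365.25/3 ≈ 122, adding about 122/28 ≈ 4.3 to an unweighted mean over 28 patients, and no bleed gives 0. Leaving a child who never starts prophylaxis out of the efficacy FAS is likewise reasonable, since there is no prophylactic period to analyse.

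SAP 3 leaves membership to the data review meeting, but neither document writes an exception for that meeting to apply.

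**Conclusion.** The point holds for the PK set. Followed as written, the nesting removes a child with a valid profile and no later IMP from the PK and PK-PP summaries for a reason unrelated to PK. The cost per child is a 95% half-width of 1.24 instead of 1.05 SD, or 1.59 instead of 1.24 SD. The number of children affected is unknown and may be zero. This assumes that the SAP's PK tables use the PK sets, as protocol 9.2.1 says; SAP 4 and 4.8 do not name the set themselves.

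The adult point is secondary. The rule is inconsistent with the ITT label and with the start of the TABR period, but the effect on the model-based ratio is negligible (at most 3 days, about 0.03% of person-time, under the assumptions above). It is a matter of a correct definition and does not threaten the primary conclusion.

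**What to change.** In SAP 3.6, replace the FAS with the SAF as the parent of the PK set. Leave the validity, diagnosis and inhibitor exclusions in SAP 3.7, where they already sit. Record the change in SAP 2.2 as a deviation from protocol 9.2.1.

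For the secondary point, define the FAS in SAP 3.2 as enrolled patients with at least one prophylactic dose of IMP, stating that in adults the dose at the Baseline IVR Visit counts, and record this in SAP 2.2 too. The trade-off is the extreme individual TABR that very short follow-up can produce. The unweighted descriptive tables should flag such patients, or be shown with and without them.

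The cost is SAP wording, set flags and the affected outputs, with no new data. Amending the protocol text itself would cost more, because protocol 10.4 requires agreement with the co-ordinating investigator and submission as regulations require; the entry in SAP 2.2 documents the change without that step. If no patient is affected, no result changes.
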